#### 7.4. Discontinuations

The criteria for enrollment must be followed explicitly. If a patient who does not meet enrollment criteria is inadvertently enrolled, that patient will continue in the study unless, in the opinion of the Sponsor's physician responsible for the study, the patient should be discontinued for safety reasons. The Sponsor or its designees must be contacted.

In addition, patients will be discontinued from the treatment period of the study in any of the following circumstances:

- if the patient experiences a loss of glycemic control, as evidenced by:
  - increase in absolute HbA1c  $\geq 0.5\%$  from baseline at 2 consecutive scheduled visits which are at least 1 month apart, prior to study completion
  - fasting blood glucose  $>250$  mg/dL (13.9 mmol/L) or non-fasting glucose  $>300$  mg/dL (16.7 mmol/L) for 4 days in a 7-day period as measured by SMBG. The patient will return to the clinic for a confirmatory fasting glucose, if possible, or a non-fasting glucose. If by local laboratory measurement a fasting glucose is  $>250$  mg/dL (13.9 mmol/L) or a non-fasting glucose is  $>300$  mg/dL (16.7 mmol/L), the patient will be discontinued from the study
- if a female patient becomes pregnant
- if the patient misses more than 10 consecutive days of study therapy
- if the patient misses more than 10 consecutive days of oral antidiabetes therapy
- if metformin or an SU is added or altered for more than 10 consecutive days or 10 days in a 30-day period after study entry
- if a patient uses excluded concomitant medications ([Section 7.2](#), Exclusion Criteria)

- if the investigator decides that the patient should be withdrawn. If this decision is made because of a serious adverse event or a clinically significant laboratory value, the study drug is to be discontinued and appropriate measures are to be taken. The Sponsor or its designee is to be notified immediately
- if the patient or attending physician requests that the patient is withdrawn from the study
- if the investigator or the Sponsor, for any reason, stops the study or stops the patient's participation in the study.

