Secondary 2	Evaluable	Change in HbA1c from baseline to Week 28 and each intermediate visit	All IEs: Data after event excluded. Hypothetical approach due to missing at random (MAR) assumption of MMRM analysis	Least squares mean difference in CFBL at Week 28 and each intermediate visit between Total EBID and PBO

	Attributes			
Estimand	Population	Variable	Intercurrent event (IE) strategy	Population-level summary
Sensitivity to secondary 2	Evaluable	Change in HbA1c from baseline to Week 28 and each intermediate visit	All IEs: Data after event excluded. Hypothetical approach using multiple imputation (MI) pattern mixture modelling	Least squares mean difference in CFBL at Week 28 and each intermediate visit between Total EBID and PBO
Continuous secondary and exploratory efficacy endpoints measured post-baseline at a single endpoint	Full analysis set	Change in XX* from baseline to Week 28	All IEs: Data after event excluded. Hypothetical approach due to missing at random (MAR) using MI ANCOVA analysis	Least squares mean difference in CFBL at Week 28 between Total EBID and PBO
Other continuous secondary and exploratory efficacy endpoints	Full analysis set	Change in HbA1c from baseline to Week 28 and each intermediate visit	All IEs: Data after event excluded. Hypothetical approach due to missing at random (MAR) assumption of MMRM analysis.	Least squares mean difference in CFBL at Week 28 and each intermediate visit between Total EBID and PBO
Exploratory	Safety	Change in eGFR from baseline to Week 28 by baseline eGFR category	All IEs: Data after event excluded. Hypothetical approach due to MAR assumption of MMRM analysis.	Least squares mean difference in CFBL at Week 28 between Total EBID and PBO
Sensitivity to exploratory	Safety	Change in eGFR from baseline to Week 28 by baseline eGFR category	Rescue and IP discontinuation: Data after event included. Treatment policy approach.	Least squares mean difference in CFBL at Week 28 between Total EBID and PBO

	Attributes			
Estimand	Population	Variable	Intercurrent event (IE) strategy	Population-level summary
			Withdrawal from study prior to Week 28: Hypothetical approach due to MAR assumption of MMRM analysis.	

*where XX are FSG, FSI, SMBG, HOMA-B, HOMA-S, hip and waist circumference.

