As a sensitivity analysis, also in the Evaluable analysis set, the probabilities of patients reaching HbA1c targets of <7%, ≤6.5%, and <6.5% will be analyzed to Week 28 using the CMH procedure, with missing data imputed using MI pattern mixture model imputation. HbA1c and background diabetes therapy strata will serve as the stratification factors. The imputed HbA1c data for the sensitivity analysis of the primary endpoint will be used for this analysis.

Similar outputs (bar chart including p-values and summary of the numbers and percentage of patients having HbA1c goals by visit and treatment group) will be produced for the Evaluable analysis set for this sensitivity analysis.

Change in body weight, FSG and FSI from baseline Visit 3 (Week 0)

The same MMRM approach (as used for the primary analysis) will be used to analyze the change in body weight from baseline Visit 3 (Week 0) to Week 28, and each intermediate visit. Baseline body weight will replace baseline HbA1c and screening HbA1c strata will be included in these models.

Since only baseline and endpoint FSG and FSI measurements are collected, these endpoints will be analyzed by multiple imputation based on the assumption that missing data are MAR via the following steps:

Step 1: Non-monotone missing data (expected to be infrequent) will be imputed using the MCMC option of SAS PROC MI with treatment, baseline FSG/FSI, screening HbA1c strata (≤8% and >8%) and background diabetes therapy strata (drug naïve, metformin only, SU only, and metformin +SU) and value of the endpoint at each visit. This will create a monotone missing pattern in the dataset within each treatment group. This step will create 1000 imputed datasets.

Step 2: After a monotone missing pattern is created for the data, PROC MI using MONOTONE REGRESSION will be used to impute missing post-baseline values. The covariates used in the model will be treatment, baseline FSG/FSI, screening HbA1c strata (≤8% and >8%) and background diabetes therapy strata (drug naïve, metformin only, SU only, and metformin +SU) and value of the endpoint at each visit. This is MAR imputation.

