Step 3: The imputed data from Step 1 and Step 2, along with observed data will be analyzed using separate ANCOVA models for each imputed dataset with change from baseline in FSG/FSI as the dependent variable and treatment, baseline FSG/FSI, screening HbA1c strata ($\leq 8\%$ and $> 8\%$) and background diabetes therapy strata (drug naïve, metformin only, SU only, and metformin +SU) as fixed effects. Parameter estimates (LS means and standard errors) and variance/covariance matrix will be obtained for each of the multiple imputed datasets.

Step 4: The estimates from multiple imputed datasets will be combined using Rubin's combination rules for statistical inference (Rubin, 1987) using PROC MI ANALYZE.

The seed used will be 88281 for both steps 1 and 2. The number of imputed datasets may be reduced depending on the extent of missing data.

The residuals from the ANCOVA model will be plotted against the quartiles from standard Normal distribution for each of the imputed datasets. A Kolmogorov–Smirnov normality test will be conducted for the residuals. If deviation from normality is noted in the ANCOVA model or imputation diagnostics including trace and autocorrelation plots indicate issues with the multiple imputation then alternative approaches will be discussed e.g. analysis of variance (ANOVA), number of imputed datasets etc.

Actual values and change from baseline will be summarized using descriptive statistics by visit and treatment group for the Full analysis set. OC summaries will be provided where appropriate.

Body weight, FSG and FSI measures will be listed.

Change in SMBG measurements from baseline Visit 3 (Week 0)

In both the seven days prior to Visit 3 (Week 0) and the seven days prior to Visit 11 (Week 28), patients will be asked to perform 4-point SMBG profiles (pre- and 2-hour post-prandial measurements at the 2 main meals of the day) on 3 separate days. SMBG profiles will be summarized as follows.

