Only complete pairs of pre-prandial and post-prandial SMBG concentrations will be used. If measurements are taken for more than 2 main meals of the day, then the latest 2 meals of the day will be used that have both a pre-prandial and post-prandial measurement. If measurements were taken on more than 3 separate days in a period, then the latest 3 days of measurements that have both a pre-prandial and post-prandial measurement prior to the visit will be used. If data are missing for a meal, then the remaining available data will be used. Thus, summary measures will be calculated provided the patient had a least one complete pair of measurements in the period.

Mean SMBG will be calculated as the mean of SMBG concentrations (pre- and post-prandial) over the 2 main meals over 3 separate days, where complete pairs of both pre-prandial and post-prandial measurements for a given meal are present. Mean SMBG at baseline Visit 3 (Week 0) and Visit 11 (Week 28) as well as the change in overall daily mean from baseline Visit 3 (Week 0) to Visit 11 (Week 28) will be summarized using descriptive statistics by treatment group for the Full analysis set.

Post-prandial excursions will be calculated as the difference between the pre-prandial and post-prandial blood glucose concentrations (post-prandial – pre-prandial) and averaged (mean) over the 2 main meals over the 3 separate days in each period. Mean post-prandial excursions at

baseline Visit 3 (Week 0) and Visit 11 (Week 28) as well as the change from baseline values will be summarized using descriptive statistics by treatment group.

The mean pre-prandial (post-prandial) SMBG concentration will be defined as the average (mean) measurement over the 2 main meals over 3 separate days in each period. Mean pre-prandial (post-prandial) SMBG concentrations at baseline Visit 3 (Week 0) and Visit 11 (Week 28) as well as the change from baseline values will be summarized using descriptive statistics by treatment group.

The same multiple imputation ANCOVA approach (as used for the analysis of FSG and FSI) will be used to analyze change from baseline Visit 3 (Week 0) to Visit 11 (Week 28) for each of the 4 SMBG summary measures (overall, pre-prandial, post-prandial, post-prandial excursions).

Change in beta-cell function (HOMA-B) and insulin sensitivity (HOMA-S) from baseline Visit 3 (Week 0) to Visit 11 (Week 28)

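### Multiple imputation for the single-endpoint glycemic secondaries only reproduces an observed-case ANCOVA (completers-only for SMBG) and ignores the interim HbA1c that triggers withdrawal

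*SAP*

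**What the plan says.** **Imputation model.** SAP 4.2.4.4 explains the method by the measurement schedule: "Since only baseline and endpoint FSG and FSI measurements are collected, these endpoints will be analyzed by multiple imputation". In Step 1, non-monotone gaps are filled by MCMC ("This step will create 1000 imputed datasets"). In Step 2, the remaining missing values come from a monotone regression: "The covariates used in the model will be treatment, baseline FSG/FSI, screening HbA1c strata", then background therapy strata, "and value of the endpoint at each visit. This is MAR imputation".

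**Analysis model.** Step 3 fits an ANCOVA with "change from baseline in FSG/FSI as the dependent variable and treatment, baseline FSG/FSI, screening HbA1c strata" and background therapy strata.

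**Reach.** For the four SMBG summary measures, "The same multiple imputation ANCOVA approach (as used for the analysis of FSG and FSI) will be used to analyze change from baseline". HOMA-B and HOMA-S are handled the same way on the log scale. Table 3 in SAP 4.2.4.1 describes the strategy for these endpoints as "Hypothetical approach due to missing at random (MAR) using MI ANCOVA analysis".

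**Withdrawal rule.** Under Protocol 7.4 a patient is withdrawn when HbA1c has risen by at least 0.5% "from baseline at 2 consecutive scheduled visits which are at least 1 month apart, prior to study completion". The schedule in Protocol Attachment 1 measures HbA1c at Weeks 4, 12, 20 and 28 and at the ED visit.

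**ED visit.** Fasting glucose and insulin are scheduled there; the pre- and post-prandial SMBG profile is not. SAP 4.2.4.4 brings ED data into the secondary ANCOVAs but excludes data after rescue or after study drug (IP) discontinuation.

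**The concern.** SAP 4.1.3.1 defines MAR as missingness that does not depend on the missing responses, given observed responses and covariates. For a regression imputation, that condition has to hold given the variables actually in the model. Here they are treatment, the baseline value and two baseline strata. Because the endpoint has no intermediate visit, including its value at each visit adds no on-treatment predictor.

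One protocol route to missingness is an observed rise in HbA1c during treatment. If the endpoint moves with HbA1c, a placebo patient withdrawn for rising HbA1c is imputed as though he or she resembled the placebo patients who kept control. Placebo then looks better than it should and the exenatide difference shrinks. The primary HbA1c MMRM uses the interim HbA1c history, and its pattern-mixture imputation conditions on the preceding visit. Only the single-endpoint secondaries discard that history, and Table 3 gives them no sensitivity estimand that would reveal the effect.

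**Working it through.** **1. The plan's own figures.** SAP 1.3 gives 122 patients randomized 2:1, difference -0.6, SD 1 and about 87% power. The standard error is sqrt(1/81.33 + 1/40.67) = 0.192, 0.6/0.192 = 3.12, and power = Φ(3.12 - 1.96) = 0.878. This reproduces the stated figure. The completer count does too: 65 × (1 - 0.23) = 50.05. The point does not depend on either; they confirm the design inputs used below.

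**2. Why the imputation adds nothing.** Let X hold the ANCOVA terms and b be the coefficients fitted to patients with an observed endpoint. Step 2 draws b* around b and imputes y = Xb* + noise. Refitting the same X to the completed data gives, on average over imputations, b again. Rubin's variance comes back close to the observed-case variance. This holds whenever the outcome alone is missing and the two models share covariates.

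Numerical check with M = 1000 on four simulated trials (81 vs 41, no ED values), estimate (SE):

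| Planned MI | ANCOVA on observed patients |
|---|---|
| -30.40 (10.67) | -30.53 (10.56) |
| -6.38 (11.45) | -6.67 (11.41) |
| -7.34 (10.50) | -7.34 (10.45) |
| -22.01 (10.82) | -22.13 (10.75) |

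In the fourth trial, giving 80% of dropouts an ED value moves both methods together, to -26.44 (MI) and -26.40 (observed cases), while completers-only stays at -22.13. The plan is therefore an observed-case analysis, and who counts as observed decides the result.

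**3. Who is observed.**
- *SMBG:* collected only in the week before Visits 3 and 11 (Protocol 6.1.3; SAP 4.2.4.4). Every discontinuer is imputed.
- *FSG, FSI, HOMA:* the Week 28 window runs from Day 2 to the last day of the treatment period (SAP 4.3.1), which for a dropout is the ED visit (SAP 3.6.6). A usable ED value becomes the Week 28 value. Not usable are values after IP discontinuation or after rescue, and ED visits not attended.

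**4. Size.** Simulation, 800 trials per scenario, 30 imputations. HbA1c effect -0.6 is from SAP 1.3, and the HbA1c withdrawal rule is from the protocol. Assumed, not in the documents: true endpoint difference -25 mg/dL, SD of change about 50, correlation r with HbA1c change of 0.3, 0.6 or 0.8, 10% other dropout, background strata shares of 20/50/10/20%. The rule removed 9% of exenatide and 24% of placebo patients; total missing was 18% and 31%. Shrinkage = (25 - |estimate|)/25.

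| Mean estimate (shrinkage) | r = 0.3 | r = 0.6 | r = 0.8 |
|---|---|---|---|
| No missing data | -24.88 | -24.95 | -25.02 |
| Planned MI, no ED values (SMBG case) | -21.95 (12%) | -19.13 (23%) | -17.27 (31%) |
| Planned MI, 50% usable ED | -23.32 (7%) | -22.54 (10%) | -22.08 (12%) |
| Planned MI, 80% usable ED | -23.94 (4%) | -23.86 (5%) | -23.86 (5%) |
| Planned MI, 100% usable ED | -24.35 (3%) | -24.68 (1%) | -24.94 (0%) |
| MI plus last observed HbA1c change, no ED values | -24.54 (2%) | -24.31 (3%) | -24.18 (3%) |

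Adding HbA1c hardly changes the mean SE without ED values (11.58 to 11.70, 11.23 to 11.23, 10.84 to 10.72). The gain is removal of bias, not extra precision. A separate simulation that entered HbA1c at Weeks 4 to 20 (true difference -1.0 mmol/L, SD 2.5, r = 0.7, no ED values) moved the estimate from -0.75 to -1.01.

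**The case against.** The strongest reply concerns FSG, FSI and HOMA. A reader might infer that these are completers-only too, and that every single-endpoint glycemic result is pulled toward zero by a quarter or more. The documents do not support that. Fasting samples are scheduled at the ED visit, fall inside the Week 28 window and enter the ANCOVA. A patient withdrawn for poor control who attends that visit contributes the poor value. With 50%, 80% and 100% of HbA1c-triggered dropouts having ED values, the mmol/L simulation gave -0.93, -1.03 and -1.07 against a true -1.0. At high ED capture the bias vanishes or changes sign. Power figures from the no-ED case (28% rising to 45% when interim HbA1c is added) therefore cannot be read as a statement about FSG.

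The post-IP exclusion does not restore the stronger reading. SAP 4.2.4.2 keeps values up to and including the discontinuation date. Completers also omit the morning injection before Visit 11, so a rule deleting every sample after the last injection would delete Week 28 values as well. But the SAP does not say which date counts as IP discontinuation, and rescued patients who stay in the study lose Week 28 with no ED sample to replace it. The share of usable ED values is therefore unknown.

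Three further limits stand. The correlations, SDs and endpoint effect are assumptions. The dropout split is also sensitive: assumed HbA1c SDs of 0.4, 0.8 and 1.0 at the early visits gave 19% placebo and 5% exenatide withdrawals. FSI, HOMA and post-prandial excursion were not simulated, and the sign of their correlation with HbA1c is not in the documents.

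A reader might also extend the point to waist and hip circumference. No rule withdraws patients on weight, and both are measured at the ED visit, so no defect is shown there.

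**Conclusion.** The structural point holds for FSG, FSI, SMBG, HOMA-B and HOMA-S: the imputation carries no information beyond an observed-case ANCOVA and omits a measured variable that drives withdrawal. This follows from the SAP text and needs no assumption.

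For the four SMBG measures the analysis rests on Week 28 completers. If SMBG change correlates with HbA1c change at 0.3 to 0.8, the estimate shrinks by roughly 12% to 31%. That range comes from a generic glucose endpoint without ED values and is illustrative.

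For FSG the bias is smaller and depends on ED capture: about 7% to 12% at 50%, about 4% at 80%, near zero at 100%. For FSI and HOMA neither size nor direction is established. These are secondary endpoints; the primary HbA1c analysis is not affected.

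**What to change.** In Steps 1 and 2 for the four SMBG measures, and also for FSG, FSI, HOMA-B and HOMA-S, add HbA1c change at Weeks 4, 12 and 20 as auxiliary variables. Use pre-rescue, on-treatment values only and order them before the Week 28 endpoint. Leave the Step 3 ANCOVA, and so the estimand, unchanged. Waist and hip need no change.

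Add one sentence stating how the ED-visit mapping and the post-IP exclusion combine, including which date counts as IP discontinuation. Report by arm how many FSG, FSI and HOMA values at Week 28 are ED values and how many are imputed.

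The cost is a few lines of SAP text and three more variables in the PROC MI list; no new data are needed. The imputation regression grows from 7 to 10 coefficients. In the simulation about 95 patients were observed (0.82 × 81 + 0.69 × 41), enough to carry that. The change should be fixed before unblinding; if that has passed, report it as a labelled supplementary analysis.

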### 6.1. Summary of Study Design

Study H8O-MC-GWBQ is a multicenter, double-blind, placebo-controlled, randomized, parallel, 3-arm trial. Approximately 195 adolescents, ages 10 to 17 years inclusive, with type 2 diabetes will be enrolled. However, the number of patients  $\geq 17$  years of age will be limited to no more than 10% of patients in each treatment arm. The patients will be naïve to antidiabetes agents, or they will be receiving oral treatment with metformin, an SU, or a combination of metformin and an SU at the time of enrollment. Randomization will be stratified by the patient's background diabetes therapy and screening HbA1c. The study will commence with a 1-week, single-blind, injectable placebo lead-in period before patients are randomly assigned to add injectable exenatide or injectable placebo to their existing diabetes treatment. Patients will be randomly assigned to 1 of 3 treatment arms: exenatide 5  $\mu\text{g}$  twice daily, exenatide 10  $\mu\text{g}$  twice daily, or placebo twice daily (volume of injection equivalent to exenatide 5  $\mu\text{g}$  or exenatide 10  $\mu\text{g}$ ). During the first 4 weeks after randomization, all patients assigned to treatment will receive exenatide 5  $\mu\text{g}$  twice daily or equivalent placebo volume twice daily. A starting dose of exenatide 5  $\mu\text{g}$  twice daily and titration to exenatide 10  $\mu\text{g}$  twice daily has been shown to mitigate the incidence of nausea. At the end of 4 weeks post-randomization, patients assigned to the exenatide 10  $\mu\text{g}$  twice daily treatment arm, or equivalent placebo volume, are then to increase their dose from 5  $\mu\text{g}$  twice daily to 10  $\mu\text{g}$  twice daily, or equivalent placebo volume. Study drug will be administered within 60 minutes before morning and evening meals (or the 2 main meals of the day, approximately 6 hours or more apart) for 28 weeks.

All patients will be expected to participate in a simplified lifestyle modification program (LMP) throughout this study ([Attachment 4](#)). The simplified lifestyle modification program will include both dietary education and physical activity components. At the clinic visits, the patients will meet with a study registered dietitian (RD) or certified diabetes educator (CDE) who will review the patient's dietary history and physical activity record. The LMP will be reinforced at each visit.

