### **6.1.2. Placebo Lead-In Period (Visit 2)**

At Visit 2, all patients who have met enrollment criteria will begin a 1-week, single-blind, injectable placebo lead-in period to familiarize the patients to injections. At this visit, patients will receive an injection pen of placebo. Patients and/or their responsible adult party (parent or legal guardian) will be instructed on how to use the injection pen. As part of the pen instruction, at this clinic visit the patient or responsible adult will inject a dose of placebo and they will be instructed that this demonstration injection has no active drug. During the 1-week lead-in period, the patients will inject study drug, placebo, SC into the abdomen within 60 minutes before the morning and evening meals (or before the 2 main meals of the day, approximately 6 hours or more apart) beginning on the evening of Visit 2. Patients will receive a glucose meter and glucose monitoring supplies for the measurement of their glucose levels during the study. Patients will be instructed on how to use the glucose meter, how to monitor their glucose, and how to recognize and treat hypoglycemia. Patients will be counseled at each visit, whether by telephone or at an actual clinic visit, by a qualified person (i.e., RD or CDE) to follow an LMP that consists of suggested standard dietary recommendations and recommended level of exercise throughout the study ([Attachment 4](#)). Patients will be asked to measure their glucose at home before and 2 hours after the beginning of the 2 main meals of the day on 3 days during the week before clinic Visits 3 and 11.

Additionally, patients' vital signs, height, pubertal status, and body weight will be measured at Visit 2 and each clinic visit through the remainder of the study. A urine pregnancy test will be performed locally on all females of child-bearing potential at Visit 2 and each clinic visit throughout the remainder of the study. If the urine pregnancy test at Visit 2 or any clinic visit throughout the remainder of the study is positive, a serum pregnancy test will be performed centrally to confirm the result.

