For approximately the first 4 weeks of therapy (until visit 5), patients assigned to both exenatide 5 µg, 10 µg and both placebo groups will inject, either exenatide 5 µg or equivalent volume of placebo, within 60 minutes before the morning and evening meals (or the two main meals of the day, approximately 6 hours or more apart). After visit 5, patients assigned to exenatide 10 µg and its matching placebo will begin injecting 10 µg twice daily.

In the week prior to Visits 3 and 11, patients will be asked to perform pre- and 2-hour postprandial blood glucose measurements at the 2 main meals of the day on 3 separate days. These glucose measurements should be recorded along with study drug dose in the patient diaries. In addition to these requested glucose measurements, patients will be encouraged to measure daily fasting glucose values at home. The diaries are considered source documents and are to be returned to the investigator at the clinic visit. If a patient fails to perform any of the aforementioned measurements, this will not constitute a protocol violation.

Also occurring at Visits 3 and 11, will be the collection of CEA and calcitonin.

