### **8.5. Selection and Timing of Doses**

Following randomization, all patients will begin administering either exenatide or placebo. Patients should inject exenatide 5 µg or the equivalent volume of placebo SC into the abdomen within 60 minutes before the morning and evening meals (or before the 2 main meals of the day, approximately 6 hours or more apart) for 4 weeks and continue administering exenatide 5 µg or placebo equivalent volume or increase their exenatide dose to 10 µg or placebo equivalent volume, according to assigned treatment. Study drug should not be administered after a meal. If a dose is missed, the treatment should be resumed with the next scheduled dose.

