6 CHANGES OF ANALYSIS FROM PROTOCOL

The CSP does not specify eGFR as an endpoint, nor is it provided by the laboratory. However, since eGFR could provide important information it will be derived and analyzed as stated in Section 4.2.4.5 of this SAP.

In addition to the protocol-specified analysis, hypoglycemia will be summarized by baseline sulfonylurea use (yes/no) and treatment.

No Generalized Linear Mixed Model (GLMM) analysis will be done using the binary HbA1c outcome (achieved vs. not achieved HbA1c goal) as the dependent variable.

No per-protocol analysis for supportive analyses will be done.

Due to the lack of data and extent of missing data, efficacy analyses will be pooled across the 5 µg and 10 µg twice daily exenatide doses for statistical testing (Total EBID). Thus, the Fisher Protected Testing produced for the primary analysis will not be required.

For the analysis of SMBG, pre and post measurement for the same meal (lunch/dinner) is changed to be generically 2 main meals (i.e. allowing breakfast) and changed to allow data from consecutive days to be used (as many patients had only consecutive days data recorded).

Due to lack of data, plasma exenatide concentrations and antibodies will only be listed.

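### On days with three complete meal pairs, the SMBG rule keeps lunch and dinner, which for a morning/evening injector replaces a dosed meal with an undosed one (minor; secondary endpoint only)

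*SAP*

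**What the plan says.** Patients are asked for readings before and two hours after the two main meals on three days in the week before Visit 3 and again before Visit 11 (Protocol 6.1.2 and 6.1.3; SAP 4.2.4.4). For days with extra data the SAP gives a rule. Its trigger is "If measurements are taken for more than 2 main meals of the day", and its action is "then the latest 2 meals of the day will be used that have both a pre-prandial and post-prandial measurement". The selected pairs feed four summary measures: overall mean, pre-prandial mean, post-prandial mean and post-prandial excursion. Each is compared between Total EBID and placebo by multiple-imputation ANCOVA.

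On injection times, Protocol 6.1 says "Study drug will be administered within 60 minutes before morning and evening meals (or the 2 main meals of the day", with the two meals at least about six hours apart. Protocol 8.5 repeats this for dosing after randomization: "within 60 minutes before the morning and evening meals (or before the 2 main meals of the day, approximately 6 hours or more apart". In the placebo lead-in, which contains the baseline SMBG week, "the patients will inject study drug, placebo, SC into the abdomen within 60 minutes before the morning and evening meals", again with the two main meals as the alternative (Protocol 6.1.2). SAP 1.2 carries the same schedule.

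SAP Section 6 reports a change to the SMBG analysis: the earlier restriction of paired readings to lunch and dinner "is changed to be generically 2 main meals (i.e. allowing breakfast").

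**The concern.** The rule selects meals by clock order, and nothing in the SAP links the selected meals to the injected ones. The drug is given before a meal. Protocol 4.1 credits a single dose with a significant reduction in the abnormal post-prandial rise, and Protocol 4.2 reports that 5 µg nearly removed post-prandial excursions in adolescents. A meal with no injection before it should therefore show less of the treatment effect. Averaging it with a dosed meal, when a second dosed meal was recorded and discarded, is expected to pull the difference from placebo toward zero.

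The rule is also applied separately in each SMBG week. A patient who records breakfast and dinner in one week and all three meals in the other is compared on different meals, which adds noise to the change score.

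SAP Section 6 presents the admission of breakfast as a deliberate change. On the days with the most complete data, the rule returns to lunch and dinner.

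**Working it through.** The documents give no power, sample size or effect figure for SMBG, so there is no stated number to reproduce. The check has two parts.

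**1. What the rule selects.** Apply it to the days with at least two complete pairs (B = breakfast, L = lunch, D = dinner):

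| Complete pairs | Kept | Undosed meal kept: morning/evening injector | Undosed meal kept: lunch/dinner injector |
|---|---|---|---|
| B, L, D | L, D | L (dosed B is dropped) | none |
| B, D | B, D | none | B |
| B, L | B, L | L | B |
| L, D | L, D | L | none |

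Only the first row comes from the latest-two rule. In the other rows nothing is discarded, and any undosed meal is there because the patient recorded it. Breakfast is still used whenever lunch or dinner lacks a complete pair.

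**2. Size for one affected patient.** Inputs from the SAP: three days and two kept meals per day, so six meals in a full patient mean. Take a patient injecting before the morning and evening meals, and let k be the number of three-meal days in the Week 28 week, the remaining days having breakfast and dinner pairs. Each three-meal day contributes one undosed meal, so

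- undosed share = k/6, that is 1/6, 2/6 or 3/6 for k = 1, 2 or 3.

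Let r be the effect at an undosed meal divided by the effect at a dosed meal. This is an assumption; the documents give no value. If the effect is the same at both dosed meals, the patient's post-prandial or excursion effect is multiplied by

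- factor = 1 − (k/6)(1 − r).

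| k | r = 0 | r = 0.25 | r = 0.5 | r = 0.75 |
|---|---|---|---|---|
| 1 | 0.83 | 0.875 | 0.92 | 0.96 |
| 2 | 0.67 | 0.75 | 0.83 | 0.92 |
| 3 | 0.50 | 0.625 | 0.75 | 0.875 |

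For example, k = 1 and r = 0.75 gives 1 − (1/6)(0.25) = 0.96, and k = 3 and r = 0 gives 1 − (3/6)(1) = 0.50.

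Selecting the two injected meals instead makes the undosed share 0 on every three-meal day. At baseline all injections are placebo, so the lost contrast arises in the Week 28 week. The effect of meal selection at baseline is on comparability between the two weeks.

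**The case against.** The other side has a good case on size. Three pairs in a day is more than the protocol asks for, and the documents do not say how often it happens. They lean toward sparse data: missed readings are not a protocol violation (Protocol 6.1.3), and one complete pair is enough for a patient to contribute (SAP 4.2.4.4). Selection works day by day, so a single three-meal day touches a sixth of a full patient mean. Patients injecting before lunch and dinner get the right meals. Selection does not depend on treatment arm, and dilution toward zero would not create a false finding of superiority. All of this stands.

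The objective (Protocol 5.2) is worded in terms of the two main meals, not the injected meals. That is correct, but Protocol 6.1 and 8.5 offer the two main meals as the alternative injection times, and neither main-meal status nor injection status corresponds to being latest in the day.

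The protocol does not say that the effect is confined to the injected meal. This also stands, and is why r is shown as a range up to 0.75.

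Three stronger readings are tempting and lack support:

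- A reader might infer that the trial's SMBG effect is halved. The factor 0.50 needs every day to be a three-meal day, no effect at all at undosed meals, and every patient on morning/evening injections. The documents establish none of these.
- A reader might see SAP 4.2.4.4 and Section 6 as flatly contradictory. They are not, because breakfast is still used on other days. The rule narrows the announced change without saying so.
- A reader might assume that injected meals can be read from the database. Protocol 6.1.3 says "These glucose measurements should be recorded along with study drug dose in the patient diaries", but the schedule in Attachment 1 transfers the injectable dose to the eCRF only for the day before Visit 11 or early discontinuation.

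**Conclusion.** The point holds, and it is minor. On days with three complete pairs, a patient on the first-named injection schedule has a dosed meal replaced by an undosed one, and nothing else in the SAP corrects this. All four SMBG measures use the selected pairs. The dilution argument applies to the post-prandial and excursion measures; no size is derived here for the overall and pre-prandial means.

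The patient-level factors rest on morning/evening injection, full three-day data, an equal effect at the two dosed meals, and the assumed r. The overall size cannot be determined, because the frequency of three-meal days, the share of morning/evening injectors and r are all absent from the documents. SMBG is a secondary endpoint, and the primary HbA1c analysis does not use these data.

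**What to change.** Replace the latest-two rule in SAP 4.2.4.4 with:

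> *If more than 2 meals have complete pairs, use the 2 meals before which study drug was injected where the database identifies them; otherwise use the morning and evening meals. Where possible, use the same meals at baseline and Week 28.*

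Align the wording with the statement in SAP Section 6 that breakfast is now admitted.

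Before unblinding, check whether meal-level injection data are in the database. If they are not, the morning/evening rule applies throughout, with the latest-two rule kept as a sensitivity summary.

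The cost is one sentence, one change to the selection program and the data check. No new data are collected and dosing is untouched. The downside is that the morning/evening fallback makes the mirror-image error for patients who inject before lunch and dinner, which is a reason to keep the sensitivity summary. The program also needs a stated convention for matching meals when they vary across the three days.
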